**CONFIDENTIAL INFORMATION**

- Assisted primary patency - Blood flow maintained through the device after implant regardless of re-interventions performed (without occlusion). Subjects who have a reintervention on a treated segment after occlusion to restore patency, or open surgical bypass to restore patency will have lost assisted primary patency at the earliest such reintervention.
- Secondary patency - Blood flow through the device (following occlusion) regardless of re-interventions performed and freedom from surgical bypass. Subjects who have open surgical bypass to restore patency of a treated segment will have lost secondary patency at the earliest such reintervention.

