**CONFIDENTIAL INFORMATION**

### 2.3.2 Secondary Endpoints

Secondary endpoints include the following:

- Technical Success, including individual components of technical success
- Device Integrity, including Individual components of device integrity
- Patency (Primary, Assisted Primary, and Secondary)
- Absence of Type I and Type III endoleaks at one month follow-up

Technical success is defined as:

- Successful access to the necessary arterial sites
- Successful deployment of all required TAMBE Device components and any required accessory components
- Patency of all required TAMBE Device components and any required accessory components on completion angiography
- Absence of surgical conversion within 24 hours of initiation of the procedure

Device integrity will be defined as freedom from all of the following events in the first year of follow-up.

- Loss of functional patency in any treated branch component due to thrombus or mechanical failure of the branch component
- Loss of functional patency in the main body component(s) due to thrombus or mechanical failure of the main body component(s)
- Separation of the treated branch components from the main body component(s)
- Separation of the main body component(s) from the accessory components (Distal Bifurcated Component Device and / or Contralateral Leg Components)

The definitions for device integrity in Appendix A of the protocol were based on the proposal outlined in Chaikof et al.[1]. These events will be adjudicated by a CEC. Device integrity and its individual components will be reported at interim follow-up time points as well, including one and six months.

Patency will be assessed using Kaplan-Meier analysis. Subjects not experiencing an event will be censored at time of last follow-up or contact. Subjects having events are defined below:

- Primary patency - Blood flow without occlusion maintained through the device after implant without an intervention. Subjects who have a reintervention on a treated segment before occlusion to prevent eventual loss of patency, after occlusion to restore patency, or open surgical bypass to restore patency will have lost primary patency at the earliest such reintervention.

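### The SAP 2.3.2 patency events are tied to procedures, so an untreated or unrestored occlusion has no event date and can be censored as patent, and a treated one is dated at the procedure

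*SAP*

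**What the plan says.** SAP 2.3.2 makes patency (primary, assisted primary, secondary) a secondary endpoint analysed by Kaplan-Meier at subject level. It introduces the events with "Subjects having events are defined below" and sets the censoring rule: "Subjects not experiencing an event will be censored at time of last follow-up or contact".

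Each bullet then has two parts.

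- Primary patency is defined as "Blood flow without occlusion maintained through the device after implant without an intervention". The next sentence lists reintervention before occlusion, reintervention after occlusion, and open bypass, and says that such subjects "will have lost primary patency at the earliest such reintervention".
- Assisted primary patency is defined as "Blood flow maintained through the device after implant regardless of re-interventions performed (without occlusion". The next sentence lists reintervention after occlusion and open bypass; such subjects "will have lost assisted primary patency at the earliest such reintervention".
- Secondary patency is defined as "Blood flow through the device (following occlusion) regardless of re-interventions performed and freedom from surgical bypass". Its event sentence lists one event only: "Subjects who have open surgical bypass to restore patency of a treated segment will have lost secondary patency at the earliest such reintervention".

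No sentence in SAP 2.3.2 gives a date to an occlusion that is seen on imaging but not followed by a listed procedure.

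**The concern.** A Kaplan-Meier analysis needs a status and a date for every subject. Here the definitions turn on blood flow, while the sentences that supply status and date turn on procedures. The two parts give different answers for the same subject. Under the event sentences, a subject whose occluded branch is reopened loses primary patency, while a subject whose branch stays closed and is left alone keeps it.

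The error runs in one direction, towards higher reported patency. Patency is a named secondary endpoint of a branched device followed to 60 months, and in a study with no hypothesis test the estimate itself is the result. Two competent analysts could draw different curves from the same data and each cite SAP 2.3.2.

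**Working it through.** The documents state no patency rate or expected number of occlusions, so there is no planned figure to reproduce. The check has three steps: compare the two parts of each bullet, size one uncounted subject, and size the dating effect.

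**Step 1. The two readings by type of case.**

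| Case | Event sentences as written | Opening definitions |
|---|---|---|
| Occlusion never treated | No event in any curve; censored as patent | Lost in all three curves; no date given |
| Occlusion reopened without bypass | Primary and assisted primary lost at the procedure; secondary retained | Primary and assisted primary lost through the occlusion; secondary retained |
| Non-bypass rescue attempted, flow not restored | Primary and assisted primary lost at the procedure; secondary censored as patent | Lost in all three curves; no date given for the secondary loss |
| Open bypass to restore patency | Lost in all three curves, at the earliest listed procedure for that curve | Lost in all three curves |

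The readings differ in status in the first and third rows. They differ in timing wherever a procedure follows an occlusion after some delay.

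**Step 2. Size of one uncounted subject.** Inputs: n=10 (Protocol Summary, number of subjects treated) and n=20 (SAP 2.2, estimated maximum). Assumptions: complete follow-up, no other events, k subjects with an untreated occlusion found at day 180. The estimate is S(t) = product over event times of (1 − d/r), where d is the number of events and r the number at risk.

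- Event sentences: no events, so S = 1.00 for any k.
- Occlusion counted at detection: S = 1 − k/n.

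| k | n=10 | n=20 |
|---|---|---|
| 1 | 1 − 1/10 = 0.90 | 1 − 1/20 = 0.95 |
| 2 | 1 − 2/10 = 0.80 | 1 − 2/20 = 0.90 |
| 3 | 1 − 3/10 = 0.70 | 1 − 3/20 = 0.85 |

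Each uncounted subject is therefore worth 10 points at n=10 and 5 points at n=20. The values of k are illustrative.

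**Step 3. Dating of a treated occlusion.** Assume one occlusion found at day 180 and treated at day 250, with all other subjects followed to day 365. At day 210 (end of the six-month ideal window in SAP Table 2) and day 242 (end of its analysis window), the primary and assisted primary curves read 1.00 under the event sentences. Dated at detection, they read 0.90 (n=10) or 0.95 (n=20). By day 365 the two rules agree. The dating error lasts only from detection to treatment; the untreated case of Step 2 is never corrected.

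**The case against.** The strongest reply is that the sentence introducing the events covers each whole bullet, including its opening definition, and that the procedure sentences never claim to be exhaustive. Read that way, an untreated occlusion already fails the primary and assisted primary definitions, and a permanently closed branch fails the secondary one. This reading is plausible. It does not close the gap, because it supplies no event date.

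A second reply is that the loss would be seen elsewhere. Device integrity in the first year counts loss of patency from thrombus or mechanical failure, needs no reintervention, and is adjudicated by the CEC (SAP 2.3.2 and 4.4). The Core Lab reports patency in every analysis window (SAP 5.4.2). The final endpoint analysis takes place once available subjects have completed 12 months (SAP 5.2), the same horizon as device integrity. All of this stands, and it limits the harm: a reader of the 12-month report would probably see the loss beside the curve. But none of these outputs feeds the Kaplan-Meier event, and after the first year the device integrity check is gone.

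A third reply is that protocol Appendix A, which is not among the documents available here, may define patency loss. The SAP cites that appendix for the safety events and for device integrity, not for the patency curves. The possibility remains open, and the fix allows for it.

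A reader might also infer that any occlusion should end secondary patency. The documents do not support that. The secondary definition expressly allows flow after an occlusion, so only an occlusion without restored flow fails it.

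**Conclusion.** The point holds as an inconsistency that should be fixed. The stated event rule omits untreated occlusion from all three curves, omits failed non-bypass rescue from the secondary curve, and dates treated occlusions at the procedure. The alternative reading counts the untreated and unrestored cases but cannot place them in time.

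The supported size is 10 points per uncounted subject at n=10, or 5 at n=20, assuming complete follow-up and no other events. How many such subjects there are is unknown. A reader might infer a larger error under attrition, since the step becomes one over the number then at risk. The documents give no attrition figures, so no larger number is claimed.

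Two further inferences should be resisted. The documents do not show that any reported curve is wrong, only that the rule permits it. Nor would such losses go unreported in the study as a whole, given device integrity and the Core Lab tables. No formal decision depends on the curves: SAP 2.4 plans no hypothesis test and SAP 5.3 no inferential analysis.

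**What to change.** Amend SAP 2.3.2 as follows.

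- **Primary and assisted primary patency:** lost at the earlier of the first image documenting occlusion of a treated segment, or the qualifying reintervention or bypass already listed for that curve.
- **Secondary patency:** lost at the earlier of open bypass, or the first image documenting an occlusion after which no restored flow is documented. State that this status is re-derived at each serial analysis, because a later image or procedure may document restored flow.
- **Source:** use the CEC-adjudicated finding where one exists, so that the curves agree with device integrity; otherwise use the imaging read.
- **Appendix A:** if it already defines patency loss, cite it in SAP 2.3.2 and align the wording.

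The Protocol Summary states that enrollment is closed. Record the change as an amendment, and also show the curves under the event sentences as now written, so that the effect of the rule is visible.

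The cost is one SAP amendment, a revised event derivation and a second set of curves. No new imaging is needed: follow-up imaging is already scheduled at one month, six months and annually (SAP 4.1), and component patency is already part of the Core Lab read (SAP 4.5). The downsides are that reported patency may be slightly lower and that the rule changes after enrollment closed. The image date is also a detection date, so it can still fall after the occlusion itself.

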#### 2.4 Statistical Hypotheses

No formal hypothesis tests will be performed.

### 3.0 Study Treatment Arms

#### 3.1 Test Arm

Patients with thoracoabdominal or pararenal abdominal aortic aneurysms are eligible for screening for participation in the study. The particular characteristics of the patient's aneurysm and anatomy will determine ultimate eligibility for enrollment. The study has been designed with standard eligibility criteria to address any known or foreseeable factors that may compromise the outcome of the clinical investigation or the interpretation of results. Only patients who meet all of the eligibility criteria will be enrolled. Anatomic criteria will be verified by the Sponsor prior to enrollment.

#### 3.2 Control Arm

There is no control arm in this clinical study.

### 4.0 Study Data Collection

#### 4.1 Study Data Collection Intervals

At the time of hospital discharge, Subjects will undergo a physical exam, a blood draw for general clinical health including BUN / Creatinine concentration and an abdominal ultrasound (optional).

Following hospital discharge, Subjects will be asked to return for follow-up visits at one month, six months, and annually for five years post-treatment. At each of these follow-up visits, Subjects will undergo an evaluation for adverse events. Evaluation methods will include a physical examination, a blood draw for BUN / Creatinine concentration, per-imaging guidelines spiral CTA of the abdomen and pelvis, and abdominal ultrasound (optional). Magnetic Resonance Angiogram (MRA) may be used as a follow-up imaging modality if the Subject is contraindicated for the required CTA follow-up. Table 1 outlines the required procedures at each follow-up visit.

**CONFIDENTIAL INFORMATION**

**Table 1: Subject Follow-up Schedule**

	Pre-Treatment	Treatment	Hospital Discharge	One Month	Six Months	Annually through 5 Years
Physical examination	X		X	X	X	X
Spiral CTA (contrast)*	X			X	X	X
Spiral CT (non-contrast)*	X			X		
Angiogram		X				
BUN / Creatinine Concentration	X		X	X	X	X
Abdominal Ultrasound (Optional)			X	X	X	X

\*Pre-Treatment CT obtained within 120 days of submission for screening, including chest, abdomen and pelvis. Abdomen and pelvis at follow-up visits.

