	
Device integrity - Absence of the following events through one year of follow-up:
 
 • Loss of functional patency in any branch component due to thrombus or mechanical failure of the branch components • Loss of functional patency in the main body component(s) due to thrombus or mechanical failure of the main body component(s) • Separation of the branch components from the main body component(s) • Separation of the main body component(s) from the accessory components (Distal Bifurcated Component and / or contralateral limb components) 
Individual components of technical success Individual components of device integrity at one month, six months and one year follow-up Patency (Primary, Assisted Primary and Secondary) Absence of Type I and Type III endoleaks at one month follow-up

Subject Population	Subjects with Thoracoabdominal Aortic Aneurysms Involving the Visceral Branch Vessels
Number of Subjects Treated	10
Number of Sites	Six in the United States
Expected Time to Complete Enrollment	18 Months
Schedule of Events	
Assessments at Pre-treatment:
 
 • CT of chest, abdomen and pelvis • Physical exam • Creatinine measurement 
Assessments at Treatment:
 
 • Angiography 
Assessments at Hospital Discharge:
 
 • Physical exam • Creatinine measurement • Abdominal ultrasound (optional) 
Assessments at Follow-up (One month, six months, and annually through 5 years):
 
 • CT of chest, abdomen and pelvis (not required at hospital discharge) • Lumbar spine series X-ray (4 views) (annual follow-up only)* • Physical exam • Creatinine measurement • Abdominal ultrasound (optional) 
*As enrollment is closed for this study, for all subjects that have completed their one year follow-up prior to this protocol amendment being implemented, subjects will be

CONFIDENTIAL INFORMATION

	expected to have radiograph assessments at their next annual follow-up exam (i.e. two year follow-up) and annually thereafter.
Anticipated Total Study Duration	7 years from initiation of enrollment

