#### 5.4.2 Core Laboratory

An independent Core Laboratory (Core Lab) will provide review of imaging data collected during the study at pre-treatment and follow-up.

Summaries of qualitative Core Lab imaging findings (endoleak, wire fracture, component separation, patency, and rupture) will be provided at each analysis window. The denominator for each category will be the number of subjects with a CT imaging assessment in the given window which is read by the Core Lab.

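### Protocol and SAP give different anatomic coverage for follow-up CT, and the Core Lab denominators do not require that a scan could show the finding being counted

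*SAP*

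**What the plan says.** **Protocol Summary, Schedule of Events.** Under "Assessments at Follow-up (One month, six months, and annually through 5 years") the imaging item is "CT of chest, abdomen and pelvis (not required at hospital discharge").

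**SAP 4.1.** For the same visits the SAP lists "per-imaging guidelines spiral CTA of the abdomen and pelvis".

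**SAP Table 1, footnote.** For follow-up: "Abdomen and pelvis at follow-up visits". The same footnote describes the baseline scan as "Pre-Treatment CT obtained within 120 days of submission for screening, including chest, abdomen and pelvis".

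**SAP 5.4.2.** On reporting: "Summaries of qualitative Core Lab imaging findings (endoleak, wire fracture, component separation, patency, and rupture) will be provided at each analysis window". On counting: "The denominator for each category will be the number of subjects with a CT imaging assessment in the given window", provided the Core Lab read it. The section sets no condition on what the scan covered and gives no category for a finding that could not be assessed.

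**The concern.** Two current documents give different instructions for the same scan. The difference does not look like shorthand, because the SAP footnote names the chest for the pre-treatment CT and then omits it at follow-up.

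The mismatch matters statistically because of how SAP 5.4.2 counts. A scan without the chest satisfies the SAP schedule and enters the denominator for all five imaging findings. If some of the device or treated aorta lies above that scan's field, the subject adds to the denominator but cannot add to the numerator for a finding in that part. Examples are a proximal Type I endoleak, a proximal wire fracture or a rupture above the field. Any such error runs in one direction, towards fewer device problems.

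Absence of Type I and Type III endoleaks at one month is a named secondary endpoint, and the SAP gives no imaging denominator other than the one in 5.4.2. SAP 5.3 limits the analysis to summary statistics, so the counts and their denominators are the result.

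**Working it through.** The plan has no test, power calculation or target rate (SAP 2.4 and 5.3), so there is no figure of its own to reproduce. The check has a textual part and an illustration.

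**1. Coverage, side by side**

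| Scan | Protocol Summary | SAP 4.1 | SAP Table 1 footnote |
|---|---|---|---|
| Pre-treatment | chest, abdomen, pelvis | not stated | chest, abdomen, pelvis |
| 1 month, 6 months, annually to 5 years | chest, abdomen, pelvis | abdomen, pelvis | abdomen, pelvis |

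The documents agree at baseline and disagree at every follow-up visit. The SAP is consistent with itself. Neither text comes from an amendment log.

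**2. Which findings could be affected**

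Only findings above an abdomen-pelvis field are at issue. The branch and distal components would be expected to lie within that field, so branch patency and distal separation are not shown to be affected.

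**3. Size of one hidden finding**

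The Protocol Summary gives 10 subjects; SAP 2.2 gives an estimated maximum of 20. If every subject has a scan in the window, one true finding that goes unseen changes the window rate by 1/10 = 10 percentage points or 1/20 = 5 percentage points. If nothing is hidden, removing an uncovered scan changes, for example, 0/10 to 0/9, and the rate stays at 0%.

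**4. Illustration with assumed coverage and assumed findings**

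Let n be subjects scanned, k true findings above the abdominal field, and c the share of scans that reach that region. Assume coverage is unrelated to having a finding.

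- Expected rate with the 5.4.2 denominator: (k × c)/n.
- Expected rate with a denominator of covering scans only: (k × c)/(n × c) = k/n, when c is above 0.

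| n | k | True rate | c | Expected reported rate under 5.4.2 | Chance that all k are missed |
|---|---|---|---|---|---|
| 10 | 1 | 10% | 1 | 10% | 0 |
| 10 | 1 | 10% | 0.5 | 5% | 5/10 = 0.50 |
| 10 | 1 | 10% | 0 | 0% | 1 |
| 20 | 2 | 10% | 1 | 10% | 0 |
| 20 | 2 | 10% | 0.5 | 5% | (10/20) × (9/19) = 0.24 |
| 20 | 2 | 10% | 0 | 0% | 1 |

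The 5.4.2 denominator multiplies the rate of findings outside the field by c. An evaluable denominator does not.

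**5. How zero findings would read**

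The upper two-sided 95% Clopper-Pearson limit for zero events in m subjects is 1 − 0.025^(1/m). For m = 20 it is 16.8%; for m = 10 it is 30.8%. If only half of 20 scans covered the region, 0/20 would look more reassuring than the 0/10 actually observed. The SAP plans no intervals; these limits only gauge how much information a zero carries.

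**The case against.** The strongest reply is that this is a wording mismatch whose effect on the results has not been shown. Most of its parts stand.

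- **Anatomy.** Nothing in the documents says where the proximal end of the device lies or how high an abdominal CT must reach. The protocol title concerns Type IV aneurysms involving the visceral branches, and SAP 3.1 also admits pararenal aneurysms. SAP 4.1 ties the CTA to imaging guidelines that are not available here and may define coverage. If the abdominal field always includes the whole device, only the inconsistency remains.
- **Scoring.** A reader might infer that unimaged territory is scored as finding-free and that the rates are therefore biased. The documents do not support that. SAP 5.4.2 fixes a denominator; it does not say how the Core Lab records a region it could not see.
- **Acquisition.** If sites scanned to the protocol schedule, the chest was covered and this counting problem does not arise. Nothing shows that any scan omitted it.
- **Device integrity.** A reader might extend the point to this endpoint. SAP 2.3.2 and 4.4 have it adjudicated by the Clinical Events Committee, which reviews reported adverse events, so the 5.4.2 denominator does not directly govern it. None of its four components is specific to the proximal end.
- **Decisions.** No test or threshold depends on these rates.

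Two things survive. The contradiction is exact. And a denominator that ignores whether the scan could show the finding is a weaker rule than one that does, which matters in a study reported only through descriptive counts.

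**Conclusion.** The concern holds as a contradiction between the Protocol Summary and the SAP on follow-up CT coverage, together with a gap in SAP 5.4.2, which has no evaluability condition. A distortion in favour of the device is possible but not demonstrated. It requires three things together: scans acquired to the SAP coverage, some device or treated aorta above the field, and a true finding there. The share of scans affected cannot be taken from the documents and could be anything from none to all. The 10-point and 5-point figures apply per hidden true finding; they do not estimate what happened. The step-4 rates rest wholly on assumed inputs. The protocol's own chest requirement and the thoracoabdominal indication make incomplete coverage plausible enough to justify a correction.

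**What to change.** 1. Reconcile the Protocol Summary schedule, SAP 4.1 and the SAP Table 1 footnote so that all state the same follow-up CT coverage. Which coverage applies is for the sponsor to decide.
2. In SAP 5.4.2, define the denominator for each finding as the subjects with a Core Lab-read CT in the window that the Core Lab recorded as evaluable for that finding. Report the number not evaluable beside each rate.
3. State whether the one-month endoleak endpoint uses this same denominator.

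The cost is SAP wording, one evaluability flag per finding in the Core Lab dataset, and possibly slightly smaller denominators. SAP 4.2 has follow-up imaging archived by the sponsor and CT scans sent to the Core Lab, so the flag could be added for scans already obtained. If every scan proves evaluable, no rate changes and the report can say so.
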